We propose a randomized trial of a multifaceted intervention designed to optimize a patient-centered approach for improving adherence to prescription opioids, “Improving the Safety of Opioid Prescriptions (ISOT).” Primary care clinicians and PACT (Patient Aligned Care Team) nurses will be randomized to ISOT or the control condition; patients will be nested by clinician status. Clinicians and PACT nurses in both groups will participate in an interactive workshop on reducing prescription opioid abuse and enhancing safety. In addition, clinicians assigned to ISOT will work with a nurse care manager (NCM) who will maintain a registry of enrolled patients, track UDT administrations and results, examine state Prescription Drug Monitoring Program data, monitor medical records, and collaborate with an internist and substance abuse specialist to provide decision support when patients demonstrate evidence of prescription opioid misuse or abuse. The NCM will also meet with intervention patients to discuss strategies for reducing opioid adverse effects and preventing diversion, and to provide rationale for prescription opioid adherence monitoring. Thus, our intervention targets system, clinician, and patient levels. A research goal is to enhance patient-centered pain care and improve the quality of the communication and relationship between the patient and the primary care team pertaining to this challenging topic. The main objectives of this study are to evaluate the efficacy and acceptability of a multifaceted intervention (ISOT) to enhance opioid safety in patients with chronic pain.

SPECIFIC AIMS

Aim 1: Evaluate to what extent a multifaceted intervention (ISOT) enhances prescription opioid safety.

Hypothesis 1: At 12 months, ISOT patients will have lower rates of prescription opioid abuse, as assessed via multiple methods (self-report, clinical interview, urine drug testing), compared to patients of clinicians randomized to the control condition.

Hypothesis 2: At 12 months, ISOT patients will experience fewer adverse events (defined in this proposal to include emergency room visits, overdoses, falls, motor vehicle accidents).

Aim 2: Assess to what extent assignment to ISOT impacts pain treatment-related processes of care.

Hypothesis 1: ISOT patients will have more modifications to clinical care documented in the medical record, including more frequent UDTs and queries to state prescription drug

monitoring programs.

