During the screening telephone call, the study research assistant will provide a brief overview of the study purpose (including clear statements that participation involves research and participation does not provide clinical treatment), review inclusion/exclusion criteria, describe what participation in the study would entail, and schedule participants for a study appointment session. If the patient is interested in participating and eligible, the patient will be scheduled for a baseline assessment (participants will also receive reminder phone calls and/or letters prior to their scheduled appointment). To enhance the likelihood of participants attending the study evaluation session, we will offer a \$50 payment in compensation for time and/or travel to attend the research visit. The baseline assessment and all follow-up evaluations will be conducted either in person or via telephone.

During the telephone screening visit, if the participant is ineligible, but is interested in receiving additional clinical services, s/he will be referred to the study PI to contact for information about relevant clinical resources.

During the assessment sessions, the research assistant will provide another overview of study participation, administer informed consent and HIPAA authorization, and instruct the participant to complete study measures.

Follow-up: In addition to the baseline assessment, all participants will complete follow-up assessments every 6 months. During these research visits, participants will complete all study measures (described below). Research visits must be completed within 1 month of the scheduled follow-ups (i.e., the 6-month follow-up must be completed between 5-7 months from baseline and the 12 month follow-up must be completed between 11-13 months from baseline).

Randomization: We will randomize by PCP; patients will be assigned to intervention or control based on randomization of their PCP and PACT nurse. At the VAPORHCS, each PACT nurse is assigned to a single PCP and each PCP has one PACT nurse. Thus, contamination effects by PACT nurses working with a PCP assigned to the control condition will not be a concern.

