Measures of Prescription Opioid Misuse/Abuse (Aim 1): The primary outcome will be responses to the Current Opioid Misuse Measure (COMM), a 17-item self-report measure that assess several constructs that place individuals at risk of opioid misuse and abuse.⁸⁰ The COMM has been well-validated⁸¹ and previously used in treatment outcome studies.³³ The COMM has also been validated for detecting prescription opioid abuse using cut-off scores ≥ 13 .⁸² The Timeline Followback (TLFB; Sobell & Sobell, 1992) is a frequently used assessment method that uses calendar prompts to elicit frequency and intensity of substance use within a specific timeframe. The TLFB has demonstrated good test-retest reliability and validity for assessing multiple substances at one time (Ehrman & Robbins, 1994; Fals-Stewart et al., 2000). This study will assess use of alcohol, marijuana, methamphetamine, cocaine, heroin, opioid medications, and other prescription medications in the past 30 days. The Structured Clinical Interview for DSM-IV(SCID) will be used to assess current alcohol and substance use disorders.⁸³ The Overdose Risk Behavior (ORB) questionnaire is a newly-developed 14-item self-report measure that assesses behaviors and activities that place an individual at higher risk of accidental overdose to prescription opioids. Participants will complete Urine Drug Tests, to evaluate for the presence of substances ingested by participants. UDTs will evaluate for cannabis, cocaine, amphetamines, benzodiazepines, barbiturates, opioids, and opiates. Confirmatory testing will be conducted for all UDT screens with unexpected results. The purpose of UDT is to have confirmation of certain prescribed and illicit substances that have been ingested by study participants. Research staff will review medical record data prior to research visits to confirm medication status. Participants will be asked to validate pharmacy data about prescription status, as well as medications prescribed outside VA.

Measures of Opioid-Related Adverse Events (Aim 1): Prior to appointments, research staff will review medical record data for participants to track adverse effects. This includes emergency room visits, falls, and overdoses. Participants will also be queried about these effects and motor vehicle accidents at each research visit.

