Aim 1: Evaluate to what extent a multifaceted intervention (ISOT) enhances prescription opioid safety. For Aim 1, we use 8.9 as an estimated standard deviation (SD) for change in COMM score from baseline to 12 months.⁹⁵ This SD estimate is based on SD's in prior intervention research.³³ For each group, an estimated SD for change was obtained using the two SD's and a within-subject intraclass correlation coefficient of 0.5. Averaging the corresponding variances leads to an estimated variance of 78 (SD=8.9). Power calculations were performed based on 28 or 32 (we may recruit as many as 40 PCPs, but do not anticipate that many will consent to participate) clinicians per intervention group and 4 or 5 patients per clinician. Table 1 displays differences in mean COMM change that can be detected under various values for the intraclass correlation coefficient. Our targeted sample size is 32 PCPs per group and an average of 5 patients per PCP. With a loss of 4 PCPs per group and 1 patient per PCP, we have power to detect small differences (able to detect $< \frac{1}{2}$ SD change) in COMM score. For Aim 1, we plan to conduct analyses for self-report data (COMM), clinical interviews to assess current substance use disorders (SCID), and results from research-administered UDTs. With n=320, 28-32 PCPs per group, and 4-5 patients per PCP, we have statistical power greater than 80% to detect differences in percentages between groups of about 20% for binary outcomes from the SCID and UDT (see Table 2 below for similar calculations for Aim 2).

Table 1. Mean differences in COMM change from baseline to 12 months (80% power, $\alpha=0.05$).

Intra-class correlation	Mean detectable difference in COMM change, n=4 patients per clinician, 28 clinicians per intervention	Mean detectable difference in COMM change, n=4 patients per clinician, 32 clinicians per intervention	Mean detectable difference in COMM change, n=5 patients per clinician, 28 clinicians per intervention	Mean detectable difference in COMM change, n=5 patients per clinician, 32 clinicians per intervention
0	3.4	3.2	3.0	2.8
0.02	3.5	3.3	3.2	2.9
0.04	3.6	3.4	3.3	3.1
0.10	3.9	3.6	3.6	3.4

Analyses for Aim 1: For comparison of mean COMM change between groups, we will use mixed longitudinal models with a random effect for PCP and patient, to allow for correlation between

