observations on different patients of the same PCP and for repeat observations on the same patient. Transformations of the outcome will be applied to meet distributional assumptions. In linear mixed models, we will include baseline measures of patient age, sex, depressive symptoms, history of SUD, and pain severity as covariates. We will also adjust for baseline COMM score and the stratification variables: PCP training type (MD/DO vs NP or PA) and proportion of clinician panel prescribed opioids (high vs low). In addition to testing formal hypotheses, we will report 95% confidence intervals for the differences in mean outcomes between groups at 6 and 12 months. For comparing the percentages classified as abusing opioids at any time during follow-up (combining information from 6 and 12 months) based on SCID and UDT, we will use generalized-linear mixed models (or GEE as needed) to incorporate correlation between patients of the same PCP. We will adjust for baseline measures of the outcome along with the covariates listed above. We will report group comparisons on all three primary outcomes (COMM, SCID, and UDT). Assuming 15% of the sample has current SUD (consistent with other research), we will not conduct interaction analyses, but will present descriptive information for each outcome (COMM, SCID, UDT) on treatment outcomes by SUD status.

Data on opioid-related adverse events will be obtained from the medical record and participant self-report. We will collect data on opioid overdoses, falls, motor vehicle accidents, and ER visits related to pain. Descriptive information on opioid-related events will be provided for each group (numbers and percentages of participants with each event). Because the number of adverse events is expected to be small, we will use Fisher's Exact test to compare adverse event percentages between groups. We will compare both percentages for each individual type of event as well as percentages of individuals experiencing any adverse event between groups.

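### Adverse-event ascertainment is tied to research visits: no chart review to month 12 is stated for participants with no later appointment, nor how they enter the Hypothesis 2 test

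*Combined protocol and SAP*

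**What the plan says.** Specific Aims states Aim 1, Hypothesis 2 as "At 12 months, ISOT patients will experience fewer adverse events", covering emergency room visits, overdoses, falls and motor vehicle accidents.

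The events come from two sources, described in Study Measures under Measures of Opioid-Related Adverse Events:

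- Chart: "Prior to appointments, research staff will review medical record data for participants to track adverse effects". "This includes emergency room visits, falls, and overdoses".
- Self-report: "Participants will also be queried about these effects and motor vehicle accidents at each research visit".

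Visits are at baseline, 6 and 12 months. The Follow-up section adds that "the 12 month follow-up must be completed between 11-13 months from baseline".

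Processes of Care Measures (Aim 2) plans a chart extraction when each patient's participation ends. It covers urine drug tests, queries to the prescription monitoring programme, and changes in care in the year before and the year during treatment. Adverse events are not in that list.

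Analyses for Aim 1 says: "Data on opioid-related adverse events will be obtained from the medical record and participant self-report". It continues: "Descriptive information on opioid-related events will be provided for each group (numbers and percentages of participants with each event"). The arms are compared by Fisher's exact test, for each event type and for any event.

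The opening of Data Analysis keeps all enrolled participants regardless of attrition. Management of Missing Data adds variables related to missingness to the models, with completer-only and multiple-imputation sensitivity analyses.

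**The concern.** Both event sources run on the visit calendar. Someone with no further appointment has no further chart review in the plan as written, although the hypothesis concerns 12 months. Death, withdrawal and loss of contact are plausibly linked to the events being counted, so the missing observation time need not be random. A fatal overdose after the last appointment is the plainest example.

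The analysis text does not close the gap. It fixes no event window and no denominator, and it gives no rule for death or withdrawal. The main missing-data method relies on covariates, which Fisher's exact test cannot take. Multiple imputation would help only if unreviewed time were recorded as missing, and nothing says it is.

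At stake is whether the Hypothesis 2 result estimates 12-month event risk in those enrolled, or something closer to event risk while participants were still being seen. By contrast, the process-of-care measures have a defined one-year window.

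**Working it through.** **1. Figures in the plan.** No event rate, dropout rate or power is given for Hypothesis 2, so there is no stated figure to reproduce. The only loss allowance is in the Aim 1 power section: "With a loss of 4 PCPs per group and 1 patient per PCP".

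- Patient-level part: 5 to 4 per PCP, so 1/5 = 20%.
- Combined with PCP loss: 32 × 5 = 160 to 28 × 4 = 112 per arm, so 1 − 112/160 = 30%.

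The 20% is used in step 2. ISOT Intervention Components, Follow-up, keeps enrolled patients of a departing clinician in the study, so a lost PCP is not a set of lost patients.

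**2. Recorded against true risk.** Let d = 0.20 be the share lost, r_c the 12-month risk in completers and r_L the risk in those lost. The risks are assumptions.

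- True risk = (1 − d)·r_c + d·r_L
- Recorded, those lost observed to month 6 (constant hazard) = (1 − d)·r_c + d·[1 − √(1 − r_L)]
- Recorded, those lost never reviewed after baseline = (1 − d)·r_c

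With r_c = 20% and r_L = 40%:

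- True: 0.8 × 20% + 0.2 × 40% = 24%
- Observed to month 6: 1 − √0.6 = 22.5%, so 16% + 0.2 × 22.5% = 20.5%
- Never reviewed: 16%

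| r_c | r_L | True | Observed to month 6 | Never reviewed | Completers only |
|---|---|---|---|---|---|
| 20% | 40% | 24% | 20.5% | 16% | 20% |
| 20% | 20% | 20% | 18.1% | 16% | 20% |
| 5% | 10% | 6% | 5.0% | 4% | 5% |

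Dropping those lost from the denominator recovers the true risk only when they have the same risk as completers (second row).

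**3. Effect on the arm comparison.** Suppose both arms have the same true risk p, participants lost have half their events missed, and they stay in the denominator. The spurious difference is p × 0.5 × (difference in loss). The null rejection rates below are for Fisher's test at 0.05 with 160 per arm, ignoring clustering. The 30% is a stress value.

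| Loss by arm | p = 5% | p = 20% | p = 40% |
|---|---|---|---|
| none | 0; 0.025 | 0; 0.036 | 0; 0.037 |
| 30% v 30% | 0; 0.023 | 0; 0.035 | 0; 0.039 |
| 30% v 15% | 0.4 points; 0.026 | 1.5 points; 0.047 | 3.0 points; 0.070 |
| 30% v 0% | 0.75 points; 0.031 | 3.0 points; 0.082 | 6.0 points; 0.169 |

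The arm losing more participants looks safer. With equal 30% loss there is no spurious difference, but power for a true 40% against 25% falls from 0.79 to 0.69, and for 20% against 10% from 0.66 to 0.57.

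**The case against.** The strongest reply is that this is a gap in the text and not a harmful rule. Several stronger readings are tempting, and the documents do not support them:

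- **Charts are read only before attended visits.** The text says neither *only* nor *attended*. A review ahead of a scheduled visit could be done even if the patient then misses it, and the analysis section names the medical record as a source without an attendance condition.
- **Dropouts are coded as event-free.** No such rule is written. It is the likely practical result of counting participants with an event over all enrolled, but exclusion or imputation has not been ruled out.
- **An overdose ends ascertainment.** Someone who survives and stays in the study would be covered by the next chart review and asked at the next visit.
- **The plan expects 30% patient dropout.** That figure includes PCP loss. The patient-level allowance is 1 in 5, and it is a power allowance and not a forecast.
- **The 11-13 month window biases the comparison.** It is a visit tolerance that applies to both arms, and no bias from it is shown.

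Telephone follow-up is also allowed, which should reduce missed visits, and the plan expects few events. All of this stands and limits the size of the problem. It does not supply a chart review for people with no later appointment. The medical utilization data in Study Measures come partly from the record, but adverse events are not named there.

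**Conclusion.** The point holds as a weakness in ascertainment and specification for an Aim 1 safety hypothesis. It does not touch the COMM outcome. For participants who die, withdraw or lose contact, the plan states no chart review to month 12 and no rule for entering them in the Fisher test. Neither keeping them with unseen events uncounted nor leaving them out recovers 12-month risk in general.

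On the assumed 20% and 40% risks with 1-in-5 loss, 24% would be recorded as about 20.5% or 16%. These risks are not in the documents, and the 16% is an extreme that requires no review at all after baseline.

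A reader might infer that the comparison is biased towards one arm. The documents do not support that: nothing in them predicts unequal loss, and with equal loss the cost is mainly lost events and power. A false difference needs unequal loss. It becomes notable when events are also common, and at a 5% event rate it stays under 1 point even at 30% against 0% loss. The change is worth making because it is cheap and removes the dependence on visits for chart-based events.

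**What to change.** Make these changes in Study Measures and Analyses for Aim 1:

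1. Extract chart-recorded emergency room visits, falls, overdoses and deaths for every enrolled participant from baseline to day 365, or to death if earlier, whether or not visits were attended. Run this alongside the planned process-of-care extraction.
2. Use that window, with all enrolled participants as the denominator, for the Hypothesis 2 comparison. Count a fatal overdose as an overdose event.
3. Report visit-based self-report separately, among those interviewed. This includes motor vehicle accidents, for which no chart source is named, so the chart-based any-event measure would not contain them and the text should say so.

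The cost is slightly more chart work. Authorization must also permit passive record follow-up after withdrawal; where it does not, the number of participants affected should be reported by arm. No extra patients or visits are needed.

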Protocol

Study Title: A Patient-Centered Intervention to Improve Opioid Safety

NCT02791399

This protocol contains the original statistical analysis plan excerpted from the funded research proposal.

04/24/2019

Details of the final protocol and recruitment outcomes are in the following publication:

A Patient-Centered Intervention to Improve Opioid Safety

SPECIFIC AIMS

With the increased use of prescription opioid medications to treat chronic pain,¹ there is growing and appropriate concern about impacts of their use. Prescription opioids are associated with increased risk of adverse medical effects, including cardiovascular events, fractures, hospitalization, and mortality.²⁻⁷ Up to two-thirds of patients prescribed opioids will exhibit some type of prescription opioid misuse, such as taking more medication than prescribed, obtaining early refills or medication from others, taking opioid for purposes other than analgesia, or sharing with friends or family.^{8,9} Prescription opioid abuse, which includes concurrent alcohol abuse or illicit substance use, occurs in 10-35% of patients with chronic pain.¹⁰ VA/DoD Clinical Practice Guidelines for patients prescribed chronic opioid therapy for pain recommend screening all patients with urine drug tests (UDT) for prescription opioid abuse and adherence prior to and during opioid therapy.¹¹ Recent reports from the VA Office of Inspector General and Under Secretary for Health additionally highlight the need to be more thorough in screening for adherence to prescription opioids. However, UDTs are currently administered to fewer than 25% of patients who initiate chronic opioid therapy.¹² Reasons for the limited use of UDTs may include clinician discomfort, uncertainty about interpreting or responding to results, and lack of clear data on effectiveness of screening to reduce prescription opioid abuse.^{13,14}

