Common adverse effects associated with opioid initiation include constipation, nausea, somnolence, and vomiting²³ and up to 50% of patients discontinue opioids due to intolerance or insufficient pain relief.^{17,23} Patients maintained on COT may be exposed to additional adverse effects, including psychosocial and medical harms.²⁴ Opioids are associated with increased likelihood of cardiovascular events, fractures, hypogonadism, sleep-related breathing disorders, and death.⁷ Unintentional overdose deaths quadrupled between 1999 and 2007, and in 16 U.S. states, more people die from prescription opioid overdose than automobile accidents.²² The dose of opioids is a major contributing factor in adverse effects^{3,4,6} and recent studies highlighted the relationship between opioid dose and elevated risk of overdose death.^{2,5}

Attempts to Reduce Harms from Prescription Opioids: Empirical studies and consensus guidelines support the routine use of urine drug tests (UDT) to assess adherence and screen for prescription opioid abuse among patients prescribed COT.²⁵⁻²⁷ The 2010 Department of Veterans Affairs Guidelines for treatment of patients prescribed COT recommend UDTs for all patients prior to initiating COT and periodic testing in stable patients. Increased frequency of UDT is recommended for patients at higher risk of abuse.¹¹ These recommendations were highlighted by recent reports from the VA Office of Inspector General and Under Secretary for

Health.²²

Despite common calls for routine screening, regular UDT is uncommon. In prior research, we demonstrated that 26% of VA patients prescribed COT receive a UDT in a one year period.²¹ Among patients at higher risk for prescription opioid abuse (such as patients with a substance use disorder), less than half receive UDT.²¹ These data replicate findings from other settings indicating UDTs are infrequently used.^{12,28-30}

Clinicians who routinely utilize UDT for all patients will encounter aberrant results in up to 40% of tests.³¹ Even among patients who appear compliant with COT, approximately 20% will test positive for an illicit drug or another non-prescribed opioid.²⁶ These findings suggest clinicians over-estimate their ability to predict risk for prescription opioid abuse. Aberrant UDT results provide an opportunity to initiate discussions about treatment adherence and may lead to safe and appropriate changes in treatment.

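### The Aim 1 adverse-event outcome leaves out death and hospitalization, and the plan does not say how a participant who dies enters the any-event percentage

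*Combined protocol and SAP*

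**What the plan says.** The opening of the Specific Aims motivates the trial by the association of prescription opioids with "increased risk of adverse medical effects, including cardiovascular events, fractures, hospitalization, and mortality". The Background repeats most of this: "Opioids are associated with increased likelihood of cardiovascular events, fractures, hypogonadism, sleep-related breathing disorders, and death".

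The adverse-event outcome is described in three places:

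- Specific Aims, Aim 1, Hypothesis 2: "defined in this proposal to include emergency room visits, overdoses, falls, motor vehicle accidents".
- Study Measures, Measures of Opioid-Related Adverse Events (Aim 1), on the record review: "This includes emergency room visits, falls, and overdoses". It continues: "Participants will also be queried about these effects and motor vehicle accidents at each research visit".
- Data Analysis, Analyses for Aim 1: "We will collect data on opioid overdoses, falls, motor vehicle accidents, and ER visits related to pain". Each event type is compared by Fisher's exact test, as are "percentages of individuals experiencing any adverse event between groups".

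The start of the Data Analysis section says that all enrolled participants are analysed whatever their attrition. The missing-data paragraph gives general handling, with completer-only and multiple-imputation sensitivity analyses. Neither mentions death.

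**The concern.** Two of the harms that justify the trial, death and hospitalization, are not components of the outcome meant to show whether the intervention is safer. The overall-significance statement in the Specific Aims says that significant results would give clinicians a treatment that lowers adverse events, and this is the outcome on which that claim would rest.

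The Processes of Care section expects that care may change after abuse is detected, including changes of opioid or dose and cessation. Serious harm or benefit in either arm is therefore possible and ought to be visible. Under the present definition, a pain-related emergency visit counts. A direct hospital admission with no listed event does not, and a death with no listed event has no stated place in the table. If deaths or admissions differed between arms, the any-event comparison could miss that or be shifted by it.

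**Working it through.** The plan gives no event rate, power or sample size for this outcome, so there is no stated figure to reproduce. The check is a comparison of the text, followed by an illustration on assumed counts.

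**1. Components.** The four events in Hypothesis 2 are emergency room visits, overdoses, falls and motor vehicle accidents. Study Measures has the first three from the record and by query, and accidents by query. Analyses for Aim 1 has the same four but limits emergency visits to those related to pain. Death and hospitalization appear in none of the three lists. Fractures and cardiovascular events are not listed either, though some fractures will enter as falls. Some admissions will enter through emergency visits, fewer if the pain-related limit applies.

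**2. How a death would be handled.** The outcome is a yes/no indicator over all enrolled participants. Three treatments of a participant who dies without a recorded listed event fit the text: scored as no event, treated as missing, or excluded. None is specified.

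**3. Ascertainment before a death.** Record review for adverse events is scheduled ahead of research appointments, and self-report happens at those visits (6 and 12 months). A participant who dies at month 3 has no later visit to report at and no appointment to trigger a review. A listed event before the death may therefore be missed. A fatal motor vehicle accident is the clearest case, since Study Measures places accidents under participant query only.

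**4. Numbers possibly affected.** Planned size: 32 PCPs per group × 5 patients = 160 per arm (Data Analysis, Aim 1). The rates below are assumptions, not from the documents.

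- Deaths at 1% to 3%: 160 × 0.01 = 1.6 to 160 × 0.03 = 4.8 per arm.
- Patients admitted at 10% to 20%: 160 × 0.10 = 16 to 160 × 0.20 = 32 per arm.
- One patient moves an arm's percentage by 1/160 = 0.6 points.

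These are upper counts. Patients who also had a listed event are already included, and the overlap is unknown.

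**5. Does the unstated rule matter?** Assume 20 of 160 (ISOT) and 32 of 160 (control) with any listed event, and further deaths with no listed event. Two-sided Fisher p-values under each treatment of those deaths:

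| Deaths, ISOT / control | Scored event-free | Counted as events | Excluded |
|---|---|---|---|
| 2 / 2 | 0.0949 | 0.1050 | 0.0945 |
| 5 / 5 | 0.0949 | 0.1193 | 0.0938 |
| 5 / 2 | 0.0949 | 0.2487 | 0.0951 |
| 2 / 5 | 0.0949 | 0.0430 | 0.0685 |

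With equal deaths the choice matters little. With an imbalance of three it can move the result in either direction, in one case across 0.05. All counts are assumed, so this shows that the rule can matter, not that it will.

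**The case against.** A trial need not adopt every harm in its background as an endpoint. This set is labelled opioid-related, it is not the primary outcome, no power is claimed for it, and the plan expects few events. The wording in Hypothesis 2 and Study Measures can be read as non-exhaustive. Medical utilization data are to be taken from the record, and healthcare use and costs will be examined if the intervention is effective. Aim 3 tests non-inferiority on pain, function, quality of life and depressive symptoms, and opioid side effects are measured. Any-cause admissions would add events that have nothing to do with opioids.

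Part of this stands. The choice of components is partly judgement, and Aim 3 covers some consequences of changing opioid treatment. But Analyses for Aim 1 states what will be collected and compared, and death and admission are not in it. The utilization examples do not mention admissions, and the cost work is conditional on effectiveness. Neither compares deaths or admissions by arm as harms.

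A reader might infer something stronger: that anyone who dies of a cause other than a recorded overdose counts as event-free. The documents do not support that. A participant who dies after a recorded fall, motor vehicle accident or qualifying emergency visit already has a counted event. Event-free scoring is also only one possible reading of a yes/no count over all enrolled participants, not a stated rule. Nor is there support for saying that the composite is dominated by its mildest component, because no component rates are given. The loss of later event opportunity after an early death is small: with an assumed imbalance of 3 deaths and an assumed 10% remaining event risk, 3/160 × 0.10 is about 0.2 points.

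**Conclusion.** The point holds in a limited form. The outcome omits death and hospitalization, which the plan itself cites as opioid harms, and gives no rule for a participant who dies. A direct admission without a recorded listed event is not counted. A death without one could be scored as event-free or dropped, and the visit-linked ascertainment may miss listed events that preceded it.

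The size and direction of any bias are unknown. The figures of about 2 to 5 deaths and 16 to 32 admitted patients per arm rest on assumed rates and take no account of overlap with listed events. Totals per arm do not show bias; that would need a difference between arms, for which the documents give no basis. This is a worthwhile, inexpensive improvement to a secondary safety comparison. It does not invalidate the trial.

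Separately, the emergency-visit component is defined two ways: all visits in Hypothesis 2 and Study Measures, pain-related visits only in Analyses for Aim 1. These must be reconciled, since the choice changes who counts as having an event.

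**What to change.** In Aim 1 Hypothesis 2, Measures of Opioid-Related Adverse Events, and Analyses for Aim 1:

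- Track all-cause death and hospital admission, with opioid-related cases flagged, from the medical record through 12 months for every enrolled participant, whether or not a visit takes place. Apply the same review to the listed events, so that those preceding a death are found.
- Report deaths and admissions by arm, each on its own line.
- Tabulate any adverse event twice: with death counted as an event, and with the present four-event set. State how a participant who dies is scored in the second table.
- Use one definition of the emergency-visit component throughout.

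The cost is small: wording changes, plus record review detached from the visit schedule. Staff already review records for this outcome, and the plan already extracts process-of-care data when each patient's participation ends. The downsides are that some events unrelated to opioids are added, which is why the four-event table is kept, and that admissions outside the VA may be incompletely captured, which should be stated when results are reported.
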